3.3 Safety Endpoint

(1) Adverse event (AE):

- **Solicited adverse event:** Including adverse events at inoculated sites (local) and non-inoculated sites (systemic) that occur within 7 days after each dose of vaccination
 - ✧ **Solicited local adverse events (inoculated sites):** tenderness/pain, induration, swelling, flush, rash, and itching
 - ✧ **Solicited systemic adverse events (including vital signs) (non-inoculated sites):** pyrexia (axillary temperature), acute allergic reaction, skin and mucosal abnormalities, diarrhea, anorexia, vomiting, nausea, cough, fatigue, irritation, and suppression.
- **Unsolicited adverse event:** Any adverse event other than solicited AEs or solicited AEs that occur outside the solicitation period.

(2) SAE: SAE that occurs from the first dose of vaccination up to 6 months after the second dose of vaccination.

(3) Adverse events of special interest (AESI): Adverse events of special interest that occur from the first dose of vaccination up to 6 months after the second dose of vaccination (including Guillain-Barré syndrome (GBS), seizure, encephalitis, myelitis, neuritis, Bell's palsy, vasculitis, and thrombocytopenia).

4 Study Design

4.1 Overall Design

This study is a multi-center, randomized, double-blind, controlled trial design. The control vaccines will be Anflu®, trivalent influenza virus split vaccines already marketed by Sinovac (including type B Victoria or type B Yamagata). This trial is a multi-center, randomized, double-blinded, and positive-controlled design. The control vaccine is Anflu®, two 0.25mL-dose trivalent influenza virus split vaccines (TIVs, containing a B Victoria lineage or B Yamagata lineage) marketed by Sinovac. This trial will be conducted on children aged 6 to 35 months with the informed consent of their guardians. A total of 3,300 participants are planned to be recruited and randomly assigned to 4 groups in a ratio of 2:2:1:1, namely the 0.25mL-dose QIV group, 0.5ml-dose QIV group, TIV-BV group, and TIV-BY group. All participants receive 2 doses of the test vaccine or control vaccine according to the 0, 28-day immunization schedule. Among them, subjects aged 6 to 11 months (before their first birthday) will receive intramuscular injections in the anterolateral thigh, and those aged 12 to 35 months will receive intramuscular injections in the deltoid muscle of the upper arm.

Table 4.1.1 Phase III Study Design

Group	Vaccine	Sample Size	Immunization schedule (days)	Antibody test blood collection point (day)
Test Group 1	Influenza Vaccine (Split Virion), Inactivated, Quadrivalent (0.25mL)	1100	0, 28	0, 56
Test Group 2	Influenza Vaccine (Split Virion), Inactivated, Quadrivalent (0.5mL)	1100	0, 28	0, 56
Control Group 1	Influenza Vaccine (Split Virion), Inactivated, Anflu (0.25mL, including BV)	550	0, 28	0, 56
Control Group 2	Influenza Vaccine (Split Virion), Inactivated, Anflu (0.25mL, including BY)	550	0, 28	0, 56
Total	\	3300	\	\

Safety evaluation: All participants are observed for immediate reactions for 30 minutes after each dose, solicited systemic and local adverse events within 0-7 days, and unsolicited adverse events within 0-28 days after each dose. Additionally, monitoring of serious adverse events (SAEs) and adverse events of special interest (AESIs) is conducted from the first dose administration to 6 months after the second vaccination to evaluate the safety.

Immunogenicity evaluation: About 2 to 3mL of venous blood is collected from each subject before vaccination and 28 days after full-course vaccination, respectively, and then the serum is isolated and

used for influenza hemagglutination inhibition (HI) antibody test to evaluate the immunogenicity of the vaccine.

4.2 Randomization

This clinical trial is a randomized, blinded, positive-controlled design. Then, random blind code will be generated by a third-party randomization statistician independent of the project using the SAS statistical software (version 9.4) according to the preset block lengths, with the subject numbers ranging from 4001 to 7300. Vaccines will be randomly assigned and blinded according to random numbers

4.3 Sample Size

This trial requires the test group: ① the non-inferiority comparison with the control groups is established and the next statistical test is carried out; ② when the absolute criteria of SCR and SPR are achieved, the trial can be considered as successful and a positive conclusion can be drawn for the test group. In this trial, when evaluating between the test group 1 (0.25-mL QIV) and test group 2 (0.5mL-QIV), the strategy of sequential test is adopted. First, test group 2 is evaluated. If the positive conclusion of test group 2 is established, test group 1 is further evaluated. Therefore, class I error correction is no longer carried out. The sample size of phase III clinical trials is estimated first by non-inferiority design, namely the QIV group is non-inferior to the TIV group. The primary endpoints of this study include two indicators: SCR and GMT. Only when the SCR and GMT of four serotypes in test group are non-inferior to the control vaccine, the investigational vaccine is considered to be non-inferior to the control vaccine. The total power is 80%, the type II error is 0.2. Based on the different sample size requirements of the two indicators, the type II error is allocated, with 0.16 for SCR comparison and 0.04 for GMT comparison.

(1) Calculation of sample size with the SCR as the indicator:

According to the results of the previous Anflu phase IV clinical trial and other literature, the SCR of the types contained in the vaccine 28 days after vaccination is over 65%, which is used as the reference proportion to estimate the sample size. The test level is taken as one-sided $\alpha=0.025$, the power of non-inferiority comparison for the SCR of a serotype is taken as $1-\beta1/4=1-0.16/4=96\%$, and the non-inferiority threshold Δ is taken as -10%. When comparing the non-inferiority of BY or BV strain, NT:NC=2:1, and PASS software is used to calculate the sample size, the test group needs 914 samples and the control group needs 457 samples. When the non-inferiority test of H1N1 or H3N2 strain is carried out, two control groups are pooled. The sample size ratio of the test group and the pooled control group is 1:1, and the test group and the pooled control group need 625 participants.

(2) Calculation of sample size with the GMT as the indicator:

Using the antibody GMT 28 days after vaccination as the outcome measure, the non-inferiority margin is $\geq 2/3$ of the 95%CI lower limit of GMT ratio between the test group and the control group, and the non-inferiority margin after logarithmic conversion is $\Delta=-0.176$. The test level is taken as one-sided $\alpha=0.025$, and the power of a certain serotype GMT for non-inferiority comparison is taken as $1-\beta2/4=1-0.04/4=99\%$, and the standard deviation after logarithmic transformation is taken as $\sigma = 0.7$ with

reference to the previous research results. When comparing the non-inferiority of BY or BV, NT:NC=2:1, and PASS software is used to calculate the sample size, the test group needs 874 samples and the control group needs 437 samples. When the non-inferiority test of H1N1 or H3N2 type is carried out, two control groups are pooled. The sample size ratio of the test group and the pooled control group is 1:1, and the test group and the pooled control group need 582 participants each.

When the SCR and GMT of the test group reach the hypothesis of non-inferiority, the absolute criteria of the SCR and seroprotection rate (SPR) of the test group are further hypothesized for test. The trial requires that the SCR and SPR of the four strains of immune antibodies reach the absolute criteria, and the total power of the trial is 80%, so the power of each test is $1 - (0.2/8) = 0.975$.

(3) Calculation of sample size with the absolute criteria of SCR:

Assuming that the SCR after vaccination is 65%, the test level is one-sided $\alpha=0.025$, the lower limit of the confidence interval of the SCR should be greater than 30%, and the power of each test is 97.5%. The sample size is calculated by PASS software, and the test group needs 28 samples.

(4) Calculation of sample size with the absolute criteria of SPR:

Assuming that the SCR after vaccination is 75%, the test level is one-sided $\alpha=0.025$, the lower limit of the confidence interval of the SPR should be greater than 60%, and the power of each test is 97.5%. The sample size is calculated by PASS software, and the test group needs 146 samples.

In consideration of the above the maximum sample size and the dropout rate of about 17%, the sample size of each test group is 1,100, and the sample size of each control group is 550, with a total sample size of 3,300.

5 Analysis Sets

(1) Immunogenicity Analysis Set

Immunogenicity analyses will be performed primarily based on the Per Protocol Set (PPS), with complementary analyses based on the Full Analysis Set (FAS) and the modified Full Analysis Set (mFAS).

➤ Modified Full Analysis Set (mFAS)

The subject population defined according to intention-to-treat (ITT) principles includes all randomized subjects who have completed the full course of vaccinations, completed blood collection prior to vaccination, and had an effective antibody titer value.

➤ Full Analysis Set (FAS)

The subject population defined according to intention-to-treat (ITT) principles includes all randomized subjects who have completed at least one vaccination, completed blood collection prior to vaccination, and had an effective antibody titer value. Subjects who are administered the vaccine erroneously will be included in the immunogenicity analysis as randomized.

➤ Per Protocol Set (PPS)

It will be a subset of FAS and included all subjects who met the inclusion criteria and did not meet

exclusion criteria, randomized and received full-course vaccination, had a blood sample collected within the time window required by the protocol, and obtained blood sample test results before/after immunization. The subjects who met the following conditions will be excluded from PPS:

- 1) Those who have significant protocol deviations (affecting immunogenicity evaluation).
- 2) Those who are vaccinated with the wrong vaccine.
- 3) Subject received a protocol-prohibited medication/vaccine.
 - Other investigational or unregistered products (drugs or vaccines) that are not investigational vaccines.
 - Use of influenza vaccines other than investigational vaccines.
 - Long-term use (for more than 14 consecutive days) of immunosuppressive or other immunomodulatory drugs (inhaled or topical steroids are allowed).
 - Immunoglobulins or blood products.
- 4) Other conditions that may affect the evaluation of immunogenicity of 28 days after full-course vaccination.

Define the above mFAS, FAS, and PPS for each type (including H1N1, H3N2, BV, and BY), respectively.

(2) Safety Set (SS)

The safety set includes all randomized subjects who have received at least one vaccination. In the safety evaluation, subjects with vaccination erroneously will be included in the statistical analysis based on the actual vaccine groups they received, according to the principle of ASaT (All Subjects as Treated).

Safety analysis will be conducted for each dose based on the actual number of vaccinations administered. The safety set for dose 1 includes all subjects who received the first dose of the investigational vaccine, which is denoted as SS1. The safety set for dose 2 includes all subjects who have received the second dose of the investigational vaccine, which is denoted as SS2.

Each analysis set will be discussed and decided by the Principal Investigator, Sponsor, statistician, and data management manager in the blind review meeting before the database is locked.

6 Statistical Considerations

6.1 General Considerations

6.1.1 General Principles

➤ Descriptive Statistics

Unless otherwise specified, the following descriptive statistical summaries will be provided based on variable types:

- ✓ Continuous variables will be statistically described using mean, standard deviation, median, quartile (Q1, Q3), minimum, and maximum values.
- ✓ Categorical or ordinal variables will be summarized using frequencies and percentages, where the number of subjects in the corresponding analysis set will be used as the denominator in the percentage calculations. The 95%CIs for percentages will be calculated using the Clopper-Pearson method.

➤ Decimal Places

Unless otherwise specified, the decimal places in the analysis report shall be executed by the following rules:

- ✓ The minimum and maximum values are consistent with the maximum number of decimal places in the original data.
- ✓ The number of decimal places in the mean, median, quartile (Q1, Q3), geometric mean, standard deviation, and 95% confidence interval is one more than the maximum number of decimal places in the original data.
- ✓ Percentages, rates, and rate differences are retained to two decimal places.
- ✓ If $P\text{-values} \geq 0.0001$ it will be reported to four decimal places. If $P\text{-values} < 0.0001$ it will be presented as '< 0.0001'.
- ✓ The test statistics of all statistical tests will be retained to three decimal places.
- ✓ Derived data should be retained to two decimal places.

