9.5 Safety follow-up observation

Observe the participants on-site for adverse events within 30 minutes after each dose of vaccination; and give the participants the diary cards after each dose to record the solicited adverse events (systemic and local) from day 0 to 7 after the vaccination and unsolicited adverse events from day 0 to 28 after the vaccination. Investigators will explain the judgment of adverse events, measurement methods, recording methods, precautions, reporting methods, etc., and distribute diary cards, rulers,

and thermometers. They will also train the participant's guardian on using the thermometer, observing adverse events, filling in the diary card, and make an appointment for the return time. Request the subject's guardian to fill out the diary card in detail from day 0 to 28 after the vaccination to record any clinical symptoms, medications and the use of other vaccines.

Conduct systematic observation 0-7 days after each dose of vaccination. The participant's guardian observes the subject's symptoms and signs every day and fill them in the diary cards for the investigators to collect safety observation data from day 0 to 7. From day 8 to 28, record the adverse events by using the method of voluntary reporting from subject's guardian and regular follow-up by investigators; and at day 28, take back the diary cards. Monitoring of SAEs and AESIs will continue until 6 months after the second of vaccination. SAEs and AESIs from day 29 after the second of vaccination to 6 months after the second will be collected through a combination of telephone follow-up once every 2 months and active reporting by the subject.

The participants should be informed of recording any adverse events at any time. In case of acute allergic reaction, Grade 3 or above adverse event or SAE, they should report to the investigators at any time and the investigators should conduct investigation, verification, and follow-up after learning until the event is resolved so as to finally complete the detailed investigation and follow-up records, which should include following:

- Description of adverse events
- Start time and end time of adverse events
- Severity classification of adverse events
- Correlation with the vaccination
- Laboratory results
- Treatment

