6.9 Safety Evaluation

The following safety evaluation will be performed based on SS.

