Meanwhile, the Kaplan-Meier method will be used to calculate the median duration of AEs and their 95% confidence intervals in each group, respectively (using the Brookmeyer & Crowley method of log-log transformation), and the log-rank test will be used to statistically test the differences between groups. The AEs after each dose of vaccination will be statistically analyzed respectively. The analysis of AEs for each dose will be based on the safety datasets of each dose.

Present the forest plots to compare the differences in the incidence rates of AEs between the two groups (test group 1 - control group 1), (test group 1 - control group 2), (test group 2 - control group 1), and (test group 2 - control group 1) according to the top ten preferred terms for incidence rates in the vaccine group.

When calculating the incidence of AEs, if the same AE occurs multiple times in the same subject, it is recorded as one occurrence. When calculating the number of events of AEs, if the same subject experiences the same AE multiple times, it is recorded multiple times. When analyzing the severity and correlation to the investigational vaccine of AEs, if the same AE occurs multiple times in the same subject, the most severe or the most relevant AE to the investigational vaccine should be selected for analysis.

Display the list of AEs related to the investigational vaccine, the list of AEs unrelated to the investigational vaccine, the list of AEs leading to drop out, and the list of Grade 3 or above AEs.

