This trial will no longer process the missing data in other immunogenicity endpoints and safety endpoints.

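### Day 0-7 reaction rates divide by every vaccinated child, so a child with no day 0-7 safety information counts as reaction-free; the bias can only be downward and is probably small

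*SAP*

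**What the plan says.** SAP 6.1.1 sets the general rule for categorical variables: "the number of subjects in the corresponding analysis set will be used as the denominator in the percentage calculations". It applies unless something else is specified.

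SAP Section 5 defines the safety sets by vaccination alone. Overall: "The safety set includes all randomized subjects who have received at least one vaccination". By dose: "The safety set for dose 1 includes all subjects who received the first dose of the investigational vaccine, which is denoted as SS1", and "The safety set for dose 2 includes all subjects who have received the second dose of the investigational vaccine, which is denoted as SS2". None of the three requires a post-dose safety record.

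SAP 6.9 applies them ("The following safety evaluation will be performed based on SS"), and 6.9.1 adds for the per-dose tables: "The analysis of AEs for each dose will be based on the safety datasets of each dose". Section 6.9.1 explains how repeated events in one child are counted, but gives no separate denominator for solicited events or for the day 0-7 window.

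SAP 6.10 imputes antibody data for the primary estimand and then closes the subject: "This trial will no longer process the missing data in other immunogenicity endpoints and safety endpoints".

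On data capture, Protocol 9.5 has the guardian observe the child daily and "fill them in the diary cards for the investigators to collect safety observation data from day 0 to 7". The same section requires a 30-minute on-site observation after each dose. Protocol 9.1 adds visits about 7 and 28 days after each dose at which safety observations are verified, and regular investigator interviews.

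Protocol 7.2 lists the incidence of adverse reactions on days 0-7 after each dose as a safety endpoint.

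**The concern.** For reactions that are actively asked about over a short window, the absence of a record is not the absence of an event. The rules above treat the two alike for any child about whom nothing was learned on days 0-7. The SAP does not say that such a child is counted as reaction-free. That is the arithmetic result of an all-vaccinated denominator combined with no handling of missing safety data.

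Two things follow. First, the error has one direction: it makes the vaccines look slightly less reactogenic than they are, on a named safety endpoint. Second, a reader could not see or correct it. The disposition summary (SAP 6.2) covers screening, completion, withdrawal and analysis sets, and the compliance summary (SAP 6.4) covers deviations, vaccination and blood collection. Neither reports how many children lack day 0-7 safety information.

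**Working it through.** The documents state no reaction incidence and no share of children without day 0-7 information, so there is no figure of the plan's own to reproduce. The calculation shows how the rule behaves over assumed values.

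**Inputs**
- N = 1,100 per test group and 550 per control group (SAP 4.3).
- p = true day 0-7 reaction incidence: assumed, 10% to 30%.
- m = share of SS1 or SS2 with no day 0-7 information by any route: assumed, 1% to 10%.
- q = reaction rate among those children: unknown.

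**Formula.** Unobserved reactions cannot be counted, so

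reported incidence = p - m × q.

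Since q cannot be negative, the reported rate cannot exceed p. If q = p,

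reported incidence = p × (1 - m).

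| True p | m = 1% | m = 2% | m = 5% | m = 10% |
|---|---|---|---|---|
| 10% | 9.9% | 9.8% | 9.5% | 9.0% |
| 20% | 19.8% | 19.6% | 19.0% | 18.0% |
| 30% | 29.7% | 29.4% | 28.5% | 27.0% |

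**Worked case.** Take N = 1,100, p = 20%, m = 5%. Children with information: 1,100 × 0.95 = 1,045. Reactions recorded: 1,045 × 0.20 = 209.
- SAP rule: 209 / 1,100 = 19.0%, Clopper-Pearson 95% CI 16.72% to 21.45%.
- Observed-data denominator: 209 / 1,045 = 20.0%, 95% CI 17.61% to 22.56%.

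The shift of 1.0 point compares with a sampling half-width of about 1.96 × √(0.20 × 0.80 / 1,100) = 2.4 points.

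**Where it would start to matter.** At p = 30%, m = 10% and N = 1,100, the SAP rule gives 27.0% with 95% CI 24.40% to 29.73%, which excludes the true 30%.

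**Between arms.** With equal true rates and equal m, both arms shrink by the same factor and the difference stays at 0. With p = 25% in both arms and m of 10% in one and 5% in the other: 0.25 × 0.95 - 0.25 × 0.90 = 23.75% - 22.50% = 1.25 points. The half-width for a difference at 25% is about 1.96 × √(0.1875 × 2/1,100) = 3.6 points for 1,100 against 1,100, and 1.96 × √(0.1875 × (1/1,100 + 1/550)) = 4.4 points for 1,100 against 550.

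**The case against.** The strongest reply is that few children will be without any information. The diary is one of several routes. The second dose is given at the visit where safety after the first is verified, and the day-56 blood is drawn at the visit where safety after the second is verified (Protocol 9.1). Missed visits are to be followed up (Protocol 10.4). This stands, and it is why m is probably small.

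Three stronger readings are tempting, and the documents do not support them:
- A reader might infer that every unreturned diary card becomes a non-reaction. It does not: a reaction noted in the 30-minute observation, at a visit or in an interview is still counted. Only a child with no information by any route is affected.
- A reader might put m at the planned dropout of about 17%, which would turn 20% into 16.6%. That allowance inflates the immunogenicity sample size (SAP 4.3) and is not a rate of missing safety information. Children who never receive dose 2 are already outside SS2.
- A reader might infer biased comparisons between arms. That needs missingness to differ by arm; the trial is double-blind and nothing in the documents suggests a difference. No safety hypothesis depends on it either: hypotheses I to VIII in SAP 6.7 all concern immunogenicity.

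It can also be said that the all-vaccinated set is a conventional safety denominator, and that an observed-data rate is unbiased only if q = p. If guardians of reacting children report more readily, it would be too high. Both points stand, and they argue for showing both rates.

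Finally, the table shells (SAP 2.1) are a separate attachment and Protocol 9.11 was not translated. Either might set another denominator; if so, the SAP text should say so. The blind review that settles the sets works from definitions with no data-availability condition.

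**Conclusion.** The point holds in a limited form. Under the SAP as written, a child with no day 0-7 safety information by any route is counted as having had no reaction, so the reported incidence can only be biased downward. The factor is (1 - m) if such children react at the same rate as the others.

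The size is not known from the documents. At assumed values of m of 2% to 5%, a true 20% is reported as 19.6% to 19.0%, a shift of 1 point or less and inside the sampling error of one arm. A distortion between arms arises only if m differs by arm, which is not shown. No primary conclusion of the trial is affected. This is a worthwhile, inexpensive improvement to a named safety endpoint, not a flaw that threatens the trial.

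**What to change.** Add to SAP 6.9.1, for adverse reactions on days 0-7 after each dose (solicited events and the overall day 0-7 endpoint alike):

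- **Denominator.** SS1 or SS2 children with any day 0-7 safety information, whether from diary, visit, interview or phone. An uneventful 30-minute observation should not qualify on its own, because every vaccinated child is due one and it covers only the start of the window.
- **Safeguard.** Always include a child with a recorded reaction, including one seen only in the 30-minute observation, so that no observed event is lost.
- **Reporting.** Give the number of children with no day 0-7 information by arm and dose.
- **Supporting analysis.** Keep the all-vaccinated SS1/SS2 rate beside the observed-data rate.
- **Unchanged.** Keep the existing safety set for SAEs, AESIs and unsolicited events after day 7.

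The cost is a few sentences, one derived flag and one supporting table. Reported rates become slightly higher and a second denominator has to be shown and labelled. The observed-data rate assumes that children without data react at a similar rate. A child with only part of the window recorded would still count as observed, so a little understatement can remain.
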